#### **7.12.6.14 Time to first rescue medication dose**

The time to first rescue medication dose, in days, will be analyzed like the time to event endpoint in [Section 7.11.6.2](#). Time to first rescue medication dose will be analyzed separately for the first 4 weeks (two groups), and the first 12 weeks (four groups). For both analysis periods, time to first rescue medication dose will be calculated relative to the date of index injection. For the primary analysis period (first 4 weeks), subjects who do not use rescue medications for the first 4 weeks will be censored at Day 29th while subjects who discontinue the study prior to the subject's Day 29th in the study will be censored at the time of discontinuation. Similarly, for the secondary analysis period, subjects who do not use rescue medication for the first 12 weeks will be censored at Day 85th while subjects who discontinue the study prior to the subject's Day 85th in the study will be censored at the time of discontinuation.

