3.4.8.2 Prior and Concomitant Medications

All prescription and non-prescription medications (eg, over-the-counter drugs and herbal supplements) that subjects report taking during the 30 days prior to the Screening Visit will be assessed and recorded in the eCRF Concomitant Medication. For each medication, documentation should list the trade or generic name, the total daily dose including units (or the dose, units and scheduled and actual frequency of administration if the medication is not taken daily), the route of administration, and the reason for use.

Concomitant medication refers to all drugs and therapies used from the time of informed consent through the EOS participation. For D1 to Week 12, rescue medication (acetaminophen) use will be recorded only in the eDiary by the subject. After W12, when the eDiary is returned to the clinic, subjects will report acetaminophen use to study staff, and reported use will be documented in the Concomitant Medication eCRF.

[Redacted]

Changes, additions, or discontinuations to medications will be assessed and recorded in the eCRF during each study visit and at the EOS/ET Visit (D169). All as needed (*pro re nata*, *PRN*) prescriptions should be converted to reflect actual number of pills and dose taken per day.

To be eligible for this study, each subject agrees that any oral, non-opioid analgesic medication regimen for or indications other than radiculopathy pain (eg, neuropathic pain, cardiac prophylaxis) will not be altered from the Screening Visit through W12. The Investigator must inform the Medical Monitor (in advance, if possible) if a subject requires analgesic medications contrary to the protocol during the study.

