## 7.2.5 Completed Subject

For the purposes of analysis, there are 3 types of completers in this trial:

- A Primary Efficacy Endpoint Completer is defined as one who receives an index injection and who has enough data to calculate data for the primary analysis period (i.e. first four weeks) regardless if Week 4 visit was completed.

- A 12-week Completer is defined as one who receives an index injection and completes the study through Week 12.
- A 24-week Completer is defined as one who receives an index injection and completes the study through Week 24.

A subject does not necessarily have to complete all visits up to Week 12, or Week 24 to be considered as a 12-week Completer or 24-week Completer respectively. As long as the Week 12 or Week 24 visits are completed, the subject will be considered as a 12-week Completer or 24-week Completer respectively.

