#### 7.3.3 Duration/Study Day/Time

Study day will be calculated as the number of days from first dose of SP-102 TF or placebo injection.

- date of event – date of first dose of SP-102 TF or placebo + 1, for events on or after first dose
- date of event – date of first dose of SP-102 TF or placebo, for events before first dose.

For all time to event analyses, subjects not reporting the specified endpoint will be censored at the time that the subjects were last known not to have experienced the endpoint. The last visit is a censoring event, and events that occur after the last visit will be disregarded in the statistical analysis. For all endpoints not encompassing death, all deaths will be treated as censoring events. In complex cases where the censoring time of the subject is uncertain, the case will be reviewed

by the Worldwide Clinical Trials (WCT) statistician and a censoring time will be assigned before database lock.

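### Time to first rescue: the SAP's fixed censoring dates ignore when the eDiary stopped and can differ from its own general last-known-event-free rule, with bias if diary lapse differs by arm

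*SAP*

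**What the plan says.** SAP 7.12.6.14 sets the censoring for time to first rescue dose. In the 4-week analysis, "subjects who do not use rescue medications for the first 4 weeks will be censored at Day 29". In the 12-week analysis, "subjects who do not use rescue medication for the first 12 weeks will be censored at Day 85". Subjects who leave before those days "in the study will be censored at the time of discontinuation". The section does not mention diary completion.

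The method is borrowed: the endpoint "will be analyzed like the time to event endpoint in" a section printed as 7.11.6.2, evidently 7.12.6.2 (time to repeat injection), which uses Kaplan-Meier quartiles and a Cox model.

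Two other places bear on this:

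- Protocol 3.4.8.2, on Day 1 to Week 12: "rescue medication (acetaminophen) use will be recorded only in the eDiary by the subject".
- SAP 7.3.3, which opens "For all time to event analyses" and continues: "subjects not reporting the specified endpoint will be censored at the time that the subjects were last known not to have experienced the endpoint". The same paragraph sends complex cases with an uncertain censoring time to the statistician, who assigns a time before database lock.

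**The concern.** A fixed-day or discontinuation censoring date is sound when the event is certain to be seen up to that date. That holds for the repeat injection, which the site gives. It does not hold for a dose that the subject takes at home and that reaches the database only through the eDiary. Once the diary stops, nothing in the visible plan shows that the subject stayed rescue-free.

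Under the endpoint rule as it would be programmed, those unobserved days enter the Cox and Kaplan-Meier risk sets as event-free time. The estimated time to first rescue is then too late. If one arm stops recording more than the other, that arm appears to delay rescue even when the treatments do not differ. The endpoint is a named secondary one, and SAP 7.12.6.19 places the other secondary endpoints in a sequential testing procedure.

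**Working it through.** **1. The two rules applied to one subject.** Take a subject with no dose recorded, a last diary entry on Day 8, and continued enrolment past Day 29.

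- SAP 7.3.3: last known event-free on Day 8, so censored on Day 8.
- SAP 7.12.6.14, reading no recorded dose as no use: censored on Day 29.
- Difference: 29 − 8 = 21 days counted as rescue-free without observation.

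A subject who stops the diary and leaves the study later is likewise carried from the last entry to the discontinuation date. With a complete diary the two rules agree.

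**2. Inputs for size.** From the documents: about 400 randomized 1:1, hence 200 per arm (the mITT set may be smaller), and a two-sided 5% level. The documents give no event rate, hazard ratio, power or lapse rate for this endpoint, so there is no printed figure to reproduce. Assumed: placebo rescue use by Day 29 of 50%, 70% or 85%; permanent diary lapse by Day 29 of 0-30% per arm; true HR 1.00 or 0.75; first rescue and lapse exponential and independent.

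**3. Formulas.** Over T = 28 days, a cumulative proportion p gives a hazard of −ln(1 − p)/28. For arm j with rescue hazard λ and lapse hazard γ:

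- Recorded-event density: f_j(t) = λ·exp(−(λ+γ)t).
- At risk, present rule: Y_j(t) = 1 − [λ/(λ+γ)]·[1 − exp(−(λ+γ)t)].
- At risk, last-entry rule: Y_j(t) = exp(−(λ+γ)t).
- The large-sample Cox log hazard ratio b solves ∫ [f₁Y₀ − f₀Y₁e^b]/[Y₁e^b + Y₀] dt = 0.
- With r = Y₁e^b/(Y₁e^b + Y₀), I = ∫ (f₁+f₀) r(1−r) dt and s = b√(200·I), rejection = Φ(−1.96 − s) + 1 − Φ(1.96 − s).

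**4. One case in full.** No true effect, 70% rescue use, lapse 30% on SP-102 and 10% on placebo.

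- λ = −ln(0.3)/28 = 0.0430; γ = −ln(0.7)/28 = 0.0127 (SP-102) and −ln(0.9)/28 = 0.0038 (placebo).
- Doses recorded by Day 29: 60.9% on SP-102 and 67.1% on placebo, although true use is 70% in both.
- Present rule: HR = 0.874, b = −0.1345, I = 0.319, s = −0.1345 × √(200 × 0.319) = −1.07, rejection 18.9%.
- Last-entry rule: HR 1.00, rejection 5.0%.

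**5. Across the assumed ranges, present rule.**

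| True HR | Lapse SP-102 / placebo | HR obtained | Rejection |
|---|---|---|---|
| 1.00 | 0 / 0, or equal 10-30% | 1.00 | 5% |
| 1.00 | 20% / 10% | 0.935-0.940 | 7-9% |
| 1.00 | 30% / 10% | 0.871-0.878 | 14-23% |
| 1.00 | 10% / 30% | 1.139-1.148 | 14-23% |
| 0.75 | equal 10-30% | 0.752-0.770 | see below |
| 0.75 | 30% / 10% | 0.663-0.666 | 74-94% |
| 0.75 | 10% / 30% | 0.859-0.877 | 16-20% |

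With equal 30% lapse and true HR 0.75, power under last-entry versus present censoring is 42.9% versus 40.7%, 57.4% versus 52.5%, and 67.5% versus 59.2% at 50%, 70% and 85% rescue use. Simulations with lapse uniform over 28 days and a median time to rescue of 4, 10 or 20 days gave similar null results at 30% versus 10%: HR 0.88-0.90, rejection 13-21%. The last-entry rule returned the true HR in the large-sample limits and 1.00-1.01 in null simulations.

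The limits depend only on the cumulative proportions. The same percentages by Day 85 would give the same figures for a two-group comparison, though the SAP's 12-week analysis uses four groups.

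**6. When lapse depends on relief.** Assume no drug effect and that only subjects who would not need rescue by Day 29 stop recording: 50% of them on SP-102, 20% on placebo. The present rule then holds its level (about 5-6%, HR 1.00). Last-entry censoring rejects about 7-8% at a median of 10 days and 11-14% at 20 days, with HR 1.06-1.12.

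**The case against.** The strongest reply is that SAP 7.12.6.14 speaks of subjects who do not use rescue, not of subjects with no dose recorded. Someone unobserved for three weeks is not a known non-user, and could fall back to 7.3.3 or to the statistician's review. A reader might therefore infer a flat contradiction and an invalid rule; the wording does not go that far for subjects still enrolled. But then 7.12.6.14 has no date for them and needs one. For subjects who discontinue, the date is explicit. The review route is for uncertain cases, and a section that already assigns a date does not clearly trigger it.

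A reader might also infer that the plan expects diaries to stop. The support is thin. The minimum of three diary days per week in 7.12.6.17 and 7.12.6.18 deals with missing scores within a week. The completer in 7.2.5 is one "who has enough data to calculate data for the primary analysis period (i.e. first four weeks) regardless if Week 4 visit was completed", so diary data are still required. Diary compliance is checked before randomization, and staff ask about medications by telephone two days after injection; neither shows rescue status after a later lapse.

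Protocol 3.4.7 and 3.5.7.7 are unreadable, so a missing-diary rule there cannot be excluded.

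It is also tempting to say that the hazard ratio will be biased, or that last-entry censoring cures it. The documents give no lapse rate, and step 6 shows that last-entry censoring can be the worse choice when relief drives the lapse. Both of these points stand.

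Finally, the testing order in 7.12.6.19 is redacted. SAP Section 11 puts PGIC 13th in the protocol order, which matches the listed sequence and suggests a late place for this endpoint, but that is inference.

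**Conclusion.** The point holds as a gap between two SAP rules with a conditional bias. For a subject whose eDiary stops before the assigned date with no dose recorded, 7.3.3 and 7.12.6.14 give different censoring dates, and 7.12.6.14 as applied treats unobserved days as rescue-free.

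There is no bias if diaries are complete, or if lapse is equal and there is no effect. With equal lapse and a true effect, the HR moves modestly toward 1. With unequal lapse unrelated to rescue need, the error favours the arm that lapses more, whichever arm that is. All sizes rest on assumed lapse and rescue rates. Severity is low to moderate: this is an other secondary endpoint, and its place in the testing order cannot be seen.

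**What to change.** In SAP 7.12.6.14, replace the censoring sentences with a rule to this effect: a subject with no recorded rescue dose is censored at the earliest of the last eDiary day on which rescue status was recorded, discontinuation, and Day 29 (4-week analysis) or Day 85 (12-week analysis). In addition:

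- State how diary gaps before that last day are handled.
- Report diary completion by arm for both periods.
- Keep the present Day 29/Day 85/discontinuation rule as a labelled sensitivity analysis.
- Correct the cross-reference from 7.11.6.2 to 7.12.6.2.

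The cost is a few lines of SAP text, one derivation and a completion summary from diary dates already collected; no new data or subjects are needed. The downside is slightly less counted follow-up and, if lapse depends on pain relief, informative censoring under the new rule. That is why both analyses should be shown together with completion by arm.

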#### **7.12.6.15 Proportion of subjects requiring rescue medication**

The proportion of subjects requiring rescue medications will be compared across treatment arms using a Chi-Square test. This endpoint will be analyzed separately for the first 4 weeks (two groups), and the first 12 weeks (four groups).

#### **7.12.6.16 Percent of rescue medication free days.**

The percent of rescue medication free days will be calculated for the primary efficacy endpoint completers as:

$$\frac{\text{Number of days without rescue medication from baseline to subject's Day 29th in the study}}{28} \times 100$$

For subjects that withdrew from the study prior to the subject's Day 29th in the study, the percent of rescue medication free days will be calculated as:

$$\frac{\text{Number of days without rescue medication from baseline to Early Termination Date}}{\text{Number of days from baseline to Early Termination Date}} \times 100$$

This will be analyzed for the primary analysis period. A one-way ANOVA model will be used to test the difference between SP-102 and the placebo arms.

**7.12.6.17 The mean change from Baseline (D1) to Week 2, Week 4, Week 8, and Week 12 in the mean morning (AM) NPRS average pain score in the affected leg**

This will be analyzed and presented using the same MMRM model described in the primary analysis, but the response variable will be change from baseline in mean weekly morning (AM) NPRS average pain score. Baseline morning NPRS average pain score is the mean of at least 5 days and no more than 7 days of morning NPRS average pain scores from the Screening visit until treatment randomization (D1). The mean weekly morning NPRS average pain score will be calculated by taking the average of the daily morning NPRS average pain scores of the seven days prior to that week. Post-baseline mean weekly morning NPRS average pain scores will be calculated as long as a week has at least 3 days with morning NPRS average pain score. If there are less than three days with morning NPRS average pain score, the mean weekly morning NPRS score will be set to missing. The mean weekly morning NPRS score will be calculated for each subject for each week up to Week 12. Change from baseline in mean weekly morning NPRS score will be calculated by subtracting the baseline value from the weekly morning NPRS score. Mean change from baseline for the first 4 weeks (with overall average) will be analyzed and presented by the treatment received for the first injection (SP-102, Placebo). Mean change from baseline for the first 12 weeks (Weeks 2, 4, 8, and 12) will be analyzed and summarized by treatment received for second injection (SP-102/SP-102, PBO/SP-102, SP-102/none, PBO/none). As part of this analysis, comparisons will test the mean LS mean differences between the following groups;

- SP-102/none vs. PBO/none
- SP-102/SP-102 vs. PBO/none
- SP-102/none vs. PBO/SP-102
- SP-102/SP-102 vs. PBO/SP-102

**7.12.6.18 The mean change from Baseline (D1) to Week 2, Week 4, Week 8, and Week 12 in the mean evening (PM) NPRS average pain score in the affected leg**

[figure not shown]
This will be analyzed and presented using the same MMRM model described in the primary analysis, but the response variable will be change from baseline in mean weekly evening (PM) NPRS average pain score. Baseline evening NPRS average pain score is the mean of at least 5 days and no more than 7 days of evening NPRS average pain scores from the Screening visit until treatment randomization (D1). The mean weekly evening NPRS average pain score will be calculated by taking the average of the daily evening NPRS average pain scores of the seven days prior to that week. Post-baseline mean weekly evening NPRS average pain scores will be calculated as long as a week has at least 3 days with evening NPRS average pain score. If there are less than three days with evening NPRS average pain score, the mean weekly evening NPRS score will be set to missing. The mean weekly evening NPRS score will be calculated for each subject for each week up to Week 12. Change from baseline in mean weekly evening NPRS score will be calculated by subtracting the baseline value from the weekly evening NPRS score. Mean change from baseline for the first 4 weeks (with overall average) will be analyzed and presented by the treatment received for the first injection (SP-102, Placebo). Mean change from baseline for the first 12 weeks (Weeks 2, 4, 8, and 12) will be analyzed and summarized by treatment received for second injection (SP-102/SP-102, PBO/SP-102, SP-102/none, PBO/none). As part of this analysis, comparisons will test the mean LS mean differences between the following groups;

- SP-102/none vs. PBO/none
- SP-102/SP-102 vs. PBO/none
- SP-102/none vs. PBO/SP-102
- SP-102/SP-102 vs. PBO/SP-102

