#### **7.12.6.13 Cumulative use of rescue medication (mg of acetaminophen)**

In this study, acetaminophen is the permitted and study-provided rescue medication. For subjects that withdraw early, their missing weekly values after withdrawal will be imputed using the average weekly score for the respective treatment group. If the subject has partial records of rescue medication on the week of subject's withdrawal, the rescue medication use on that week will be imputed as follows:

[ partial record of rescue medication on the withdrawal week \* (7/number of days in the withdrawal week with partial record) ].

Cumulative use of rescue medication at Week 4 will be obtained as the rescue medication use during the first four weeks relative to the index injection, that is, up to the subject's Day 29 in the study. It will be analyzed using an analysis of variance (ANOVA) model with cumulative use from baseline to Week 4 as the response variable with fixed effects for treatment (two groups: SP102 or placebo), site, and Pain Catastrophizing Scale group ( $<30$  or  $\geq 30$ ). The same ANOVA model will

be applied on only subjects that complete 4 Weeks and output will be presented using the two treatment groups.

Cumulative use of rescue medication at Week 12 will be obtained as the rescue medication use during the first 12 weeks relative to the index injection, that is, up to subject's Day 85 in the study. It will also be analyzed using an ANOVA model with cumulative use from baseline to Week 12 as the response variable with fixed effects using the four treatment (SP-102/SP-102, PBO/SP-102, SP-102/none, PBO/none) variable, site, and Pain Catastrophizing Scale group (<30 or ≥30). The same ANOVA model will be applied on only subjects that complete 12 Weeks and output will be presented using the four treatment groups.

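### The two formulas for percent of rescue-free days do not divide the subjects cleanly, and the fixed divisor of 28 makes the score depend on diary adherence

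*SAP*

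**What the plan says.** SAP 7.12.6.16 defines the endpoint in two parts.

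- **Completer formula.** "The percent of rescue medication free days will be calculated for the primary efficacy endpoint completers as" a ratio with numerator "Number of days without rescue medication from baseline to subject's Day 29th in the study" and divisor 28, times 100.
- **Withdrawal formula.** "For subjects that withdrew from the study prior to the subject's Day 29", the same kind of count up to the termination date is divided by "Number of days from baseline to Early Termination Date".

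The arms are then compared by one-way ANOVA. The opening of SAP 7.12.6 puts this endpoint, like the other secondary ones, in the mITT and PP populations.

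Four other places bear on it:

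- SAP 7.2.5 defines the primary efficacy endpoint completer as a subject given the index injection "who has enough data to calculate data for the primary analysis period (i.e. first four weeks) regardless if Week 4 visit was completed". Protocol 5.2.3 had required completion through Week 4, and SAP section 11 records the change.
- SAP 7.3.3 sets the study day as "date of event – date of first dose of SP-102 TF or placebo + 1, for events on or after first dose", so the injection day is Day 1.
- Protocol 3.4.8.2: "For D1 to Week 12, rescue medication (acetaminophen) use will be recorded only in the eDiary by the subject". The visible text names no second source for a missing day.
- SAP 7.12.6.13 takes Week 4 cumulative use as "rescue medication use during the first four weeks relative to the index injection, that is, up to the subject's Day 29 in the study". It scales up a partly recorded withdrawal week, but shows no rule for unrecorded days in subjects who remain.

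**The concern.** Under the protocol's definition of a completer, the two formulas come close to dividing subjects into those who reached Week 4 and those who left. Once the completer is defined by data sufficiency, that division is lost. A subject who leaves shortly before Day 29 with enough data fits both formulas, and no precedence rule is stated. A subject still in the study at Day 29 without enough data fits neither, although the mITT analysis needs a value.

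Separately, the completer formula divides by 28 however many days were recorded, and the SAP does not say whether an unrecorded day counts as rescue-free. The counting window in the numerator is also not tied to the divisor.

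The result is a tested endpoint whose value reflects diary adherence and the choice of formula as well as rescue use. Two programmers working faithfully from the section could produce different data sets and different p-values.

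**Working it through.** **1. The plan's 28.** As elapsed days, 29 − 1 = 28, and 4 × 7 = 28, so the figure is reproduced. As an inclusive count under SAP 7.3.3, Day 1 to Day 29 is 29 days. The numerator wording excludes neither end. With both ends counted and no rescue use, the score is 29/28 = 103.6%, and one rescue day still gives 28/28 = 100%. With one end dropped, the maximum is 28/28 = 100%. The withdrawal formula has the same looseness: for Day 25, 25/25 = 100% if both parts are counted alike, and 25/24 = 104.2% if the divisor is a date difference.

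**2. Overlap.** Take a subject who withdraws on Day 25, has every day to then recorded, and has enough data to be a completer. Count Day 1 as the first day. Rule A counts Days 26 to 28 as rescue-free. Rule B does not count them.

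| Rescue days | Completer formula, Rule A | Completer formula, Rule B | Withdrawal formula |
|---|---|---|---|
| 0 | 28/28 = 100% | 25/28 = 89.3% | 25/25 = 100% |
| 12 | 16/28 = 57.1% | 13/28 = 46.4% | 13/25 = 52.0% |

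With no rescue use, the formulas disagree only under Rule B. With 12 rescue days they disagree under either rule, in opposite directions.

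**3. Gap.** A subject who stays to Day 29 without enough data is not a completer under SAP 7.2.5 and did not withdraw before Day 29. No formula applies.

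**4. Unrecorded days in a subject who stays (28-day window, 7 days unrecorded).**

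- No rescue on the 21 recorded days: 28/28 = 100% if unrecorded days count as rescue-free, 21/28 = 75% if they do not.
- Rescue on all 21 recorded days: 7/28 = 25% if they count as rescue-free, although the recorded days show 0%; 0/28 = 0% if they do not.

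The first rule understates rescue use and the second understates rescue-free time. Under either, the score moves with adherence.

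**5. Scale of the overlap in an arm mean.** The share of an arm in the overlap is not given, so 2% to 17% is assumed. The top of the range is the whole planned Week 4 shortfall, (400 − 332)/400 = 17%, and is an outer limit, not an estimate. With no rescue use and Rule B:

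- Day 25 withdrawals: the formulas differ by 100 − 89.3 = 10.7 points, so the arm mean moves by 0.2 to 1.8 points.
- Day 15 withdrawals: 15/28 = 53.6%, a difference of 46.4 points, so it moves by 0.9 to 7.9 points. This needs a data threshold lax enough to make a Day 15 withdrawal a completer.

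**The case against.** The strongest reply has four parts.

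*The 28 is right and scores cannot exceed 100%.* A reader might infer from Day 1 and Day 29 that the divisor is wrong. The documents do not support that, because 28 is correct as elapsed days and Day 2 to Day 29 gives a maximum of 100%. What stands is that the window is not stated, so 103.6% is possible under the inclusive count but not certain.

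*The withdrawal formula is plainly the exception to the general one.* That is a sensible reading and would settle the overlap. The SAP does not state it, and it does nothing for the gap or for unrecorded days.

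*The threshold for enough data may lie in redacted text.* This is true, and the redaction is no fault of the plan. It limits what can be said about size. A lax threshold enlarges the overlap and shrinks the gap, and a strict one does the reverse, so both cannot be large. A reader might also infer that missing one week's data removes completer status, but no visible text says so. Wherever the threshold sits, the groups are still defined on two different criteria.

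*Unrecorded days and attrition.* Two further inferences go too far. One is that unrecorded days do count as rescue-free under the plan: the SAP is silent, and the 89.3% figure needs the opposite rule. The other is that 17% of subjects are affected: that is the planned allowance for all Week 4 non-completion, most of which need not fall in the overlap.

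**Conclusion.** The point holds as a defect of definition in one other-secondary endpoint. The two formulas rest on criteria that are neither mutually exclusive nor exhaustive, and a fixed divisor of 28 applied to completers defined by data makes the score depend on adherence whichever way unrecorded days are read.

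For an individual subject the effect can be about 11 points (Day 25 withdrawal, no rescue, later days not counted) or 25 points (7 unrecorded days). For an arm mean, the overlap alone is worth 0.2 to 1.8 points for Day 25 withdrawals under the assumed shares. The true shares cannot be derived from the documents.

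Bias in the arm comparison arises only if adherence or withdrawal differs by arm; otherwise the cost is noise and an irreproducible derivation. The primary and key secondary results are unaffected. SAP 7.12.6.19 applies sequential testing to the other secondary endpoints, but the order is not visible, so the effect on the test sequence cannot be judged.

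**What to change.** Replace both formulas with one, for every mITT subject with at least one recorded day and likewise in the PP population:

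100 × (recorded eDiary days with no acetaminophen) / (recorded eDiary days)

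- Count numerator and divisor over the same 28-day window, for example from after the injection on Day 1 to Day 28, truncated at withdrawal or repeat injection if earlier.
- Define a recorded day and a minimum number of recorded days, and report by arm how many subjects fall below it.
- Use the same window for Week 4 cumulative rescue use, so that observed totals cover the same four 7-day weeks as the imputed ones.
- Add a sensitivity analysis that counts unrecorded days as rescue days.

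With this formula the maximum is 100%. The Day 25 subject with all days recorded and Day 25 counted scores 25/25 = 100% with no rescue and 13/25 = 52.0% with 12 rescue days, whatever the completer status. The subjects with 7 unrecorded days score 21/21 = 100% and 0/21 = 0%.

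The cost is a few lines of SAP text and programming before unblinding, with no new data. Subjects with few recorded days get noisier values, and unrecorded days are assumed to resemble recorded ones, which is why the sensitivity analysis is worth having. Time to first rescue dose (SAP 7.12.6.14) is censored at Day 29. Either align it or note the one-day difference; a Day 2 to Day 29 window would also match the divisor.
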